5 STUDY OBJECTIVES

5.1 PRIMARY

The primary objective of this study is to assess the long-term safety of alirocumab when added to currently available lipid-modifying drug therapy, in patients diagnosed with heterozygous Familial Hypercholesterolemia who have completed one of the four parent studies.

5.2 SECONDARY

The secondary objectives of this study are

- To evaluate the long-term efficacy of alirocumab on lipid parameters
- To evaluate the long-term immunogenicity of alirocumab

6 STUDY DESIGN

6.1 DESCRIPTION OF THE PROTOCOL

This is a multicenter, multinational, Phase 3, open-label extension, uncontrolled study to assess the long-term safety and efficacy of alirocumab, when added to currently available LMT, in heFH patients previously participating in the ODYSSEY FH I, ODYSSEY FH II, ODYSSEY High FH or ODYSSEY Long Term studies.

Patients must have been diagnosed with heFH in the parent study, have completed one of the above parent studies, and be willing to participate in the ODYSSEY OLE study. Patients who missed the last injection or who performed the end of treatment visit outside the expected timelines can also be enrolled.

The visit 1 (Day 1) of the ODYSSEY OLE study corresponds to:

- the end of treatment visit of the Double-Blind Treatment Period for the patients enrolled in one of the three following parent studies ODYSSEY FH I, ODYSSEY FH II, ODYSSEY High FH.
- the end of study visit, after the 8 week follow-up period, for the patients having participated in the ODYSSEY Long Term study.

Patients who meet eligibility criteria at the visit 1 (Day 1) will receive the first SC injection of alirocumab in the clinic on the same day.

In addition, patients from the ODYSSEY Long Term study will have the possibility to perform a placebo, self-injection training, before the first alirocumab administration using an auto-injector on that same day (Day 1), as they used a different device (a prefilled syringe) in the parent study.

At entry in the ODYSSEY OLE study, visit 1 on Day 1:

- All eligible patients from ODYSSEY High FH will get the alirocumab 150 mg dose.
- All eligible patients from ODYSSEY FH I, ODYSSEY FH II and ODYSSEY Long Term will get alirocumab 75 mg.

From Week 12 (Visit 4), the Investigator will manage, based on his/her own judgment and LDL-C values, adjustment of alirocumab doses (either up-titration from 75 to 150 mg every 2 weeks or down-titration from 150 to 75 mg every 2 weeks, or maintenance of the dose, will be possible).

The study consists of:

- An open-label treatment period with alirocumab of up to 168 weeks, ie approximately 3.5 years, for the first patients enrolled, or until the product becomes commercially available for the patient in the country, whatever comes first.
- A post-treatment safety follow up period of 10 week-duration after last IMP injection for all the patients, the patients who will complete the study and the patients who will early discontinue whatever the reason.

Although the background therapies, statin at MTD or other LMT (if applicable), should be maintained stable if possible, they might be adjusted based on Investigator judgment, in particular in case of tolerability issue. The reasons of any adjustment should be documented and recorded in the e-CRF.

For adjustments based on LDL-C values, simultaneous adjustments in alirocumab dose and any LMT should be avoided.

Patients will be asked to continue to follow a stable diet (equivalent to the National Cholesterol Education Program Adult Treatment Panel III Therapeutic Lifestyle Changes (NCEP ATP III TLC) during the study.

Patients will return for regular on site visits according to the flow chart for additional laboratory testing, questionnaires, clinical examination and IMP dispensation.

6.2 DURATION OF STUDY PARTICIPATION

6.2.1 Duration of study participation for each patient

The OLE study is planned to be completed in second quarter 2017 which corresponds to a study duration of approximately 168 weeks for the first patients enrolled or until the drug is commercially available for the patient in the respective country, whatever comes first. For patients in the UK, the study will last a maximum of 176 weeks.

The study duration includes up to approximately 3.5 years of treatment for the first patients enrolled, and 10 weeks of follow up after the last IMP injection for all the patients, those who will complete the study and those who will early discontinue whatever the reason.

The study will be considered as completed for a patient in the following situations:

- When the alirocumab is commercially available in the patient's country
- In second quarter 2017, if alirocumab is not yet commercially available in the patient's country

An EOT visit will be done 2 weeks after the last IMP injection and a safety follow up call 10 weeks after the last IMP injection.

The following situations will be considered as premature discontinuation of the patient from the study:

- Any withdrawal from the study to switch to an anti-PCSK9 inhibitor different from commercial alirocumab
- Any other reason

An unscheduled visit should take place within 5 days after the last IMP administration if possible, with assessments normally planned at the EOT visit, and a safety follow up call performed 10 weeks after the last IMP injection (see section 10.3.4).

The end of study per patient is the last protocol planned call. Patients with a Serious Adverse Events (SAEs) or an Adverse Event of Special Interest (AESI) should be followed until resolution, stabilization, or death.

6.2.2 Determination of end of clinical trial (all patients)

The end of the study is scheduled to be in second quarter 2017, including in the UK, which corresponds to the last protocol planned call of the last patient.

6.3 INTERIM ANALYSIS

Interim analyses might be performed if requested by Health Authorities or if needed for the purpose of scientific communication.

6.4 STUDY COMMITTEE

Data Monitoring Committee:

An independent Data Monitoring Committee (DMC), composed of members who are independent from the Sponsor and the study Investigators, is implemented in order to monitor patient safety by conducting formal reviews of accumulated safety data. The DMC will provide the Sponsor with appropriate recommendations on the conduct of the clinical trial to ensure the protection and safety of the patients enrolled in the study.

All activities and responsibilities of the DMC are described in the DMC charter.

7 SELECTION OF PATIENTS

7.1 INCLUSION CRITERIA

- I 01. Eligible patients for this OLE study will be patients diagnosed with heFH in the parent study and who have completed one of them: ODYSSEY FH I, ODYSSEY FH II, ODYSSEY High FH or ODYSSEY Long Term studies. Patients who missed the last injection or who performed the end of treatment visit outside the expected timelines can also be enrolled.
- I 02. Signed written informed consent

7.2 EXCLUSION CRITERIA

Patients who have met all the above inclusion criteria listed in Section 7.1 will be screened for the following exclusion criteria which are sorted into the following 3 subsections:

7.2.1 Exclusion criteria related to study methodology

- E 01. Significant protocol deviation in the parent study based on the Investigator judgment, such as non-compliance by the patient
- E 02. Any patient who experienced an adverse event leading to permanent discontinuation from parent study
- E 03. Patients having any new condition or worsening of existing condition which in the opinion of the Investigator would make the patient unsuitable for enrollment, or could interfere with the patient participating in or completing the study
- E 04. Patients who will be prescribed fibrates, other than fenofibrate

7.2.2 Exclusion criteria related to the background therapies

E 05. All contraindications to the background therapies or warnings/precautions of use (when appropriate) as displayed in the respective National Product Labeling

7.2.3 Exclusion criteria related to the current knowledge of alirocumab

- E 06. Known hypersensitivity to monoclonal antibody or any component of the drug product
- E 07. Positive pregnancy test at last visit of the parent double-blind study (Day 1, Visit 1)

E 08. Women of childbearing potential not willing to continue highly-effective method(s) of birth control (as defined in the informed consent form and/or in a local protocol addendum) and/or who are unwilling or unable to be tested for pregnancy

Note: Women of childbearing potential must have a confirmed negative pregnancy test at Visit 1 at entry in the OLE. They must use an effective contraceptive method throughout the entire duration of the study treatment, and for 10 weeks after the last injection of IMP, and agree to repeat urine pregnancy test at designated visits. The applied methods of contraception have to meet the criteria for a highly effective method of birth control according to the "Note for guidance on non-clinical safety studies for the conduct of human clinical trials for pharmaceuticals (CPMP/ICH/286/95)" (11).

Postmenopausal women must be amenorrheic for at least 12 months.

8 STUDY TREATMENTS

8.1 INVESTIGATIONAL MEDICINAL PRODUCT

Sterile alirocumab drug product will be supplied at a concentration of 75 mg/mL and 150 mg/mL in histidine, pH 6.0, polysorbate 20, and sucrose, both as 1 mL volume in an auto-injector (AI).

Unlike the patients from the other studies, the patients from the ODYSSEY Long Term study used a different device (a prefilled syringe) in the parent study, and thus will have the possibility to perform on Visit 1 (Day 1) a placebo, self-injection training, using an auto-injector, before the first alirocumab administration.

Injection for training: Sterile placebo for alirocumab will be prepared in the same formulation as alirocumab without the addition of protein as 1 mL volume in an auto-injector, for those patients willing to perform injection training.

Note: Only in the event the manufacturer faces any performance or supply issues of the auto-injector, contingency alternatives are the following ones, in order to ensure the continuity of the study treatment without interruption:

- In case of disruption of the 150 mg auto-injector, and the use of 75 mg auto-injectors is maintained:
 - patients receiving the 150 mg dose will need to administer 2 injections of 75 mg as 1 mL each in an auto-injector,

OR

- patients will be switched to the use of prefilled syringes of 150 mg, with one injection of 1 mL.
- In case of disruption of either 75 mg or both auto-injectors, patients will be switched to the use of prefilled syringes of 75 mg and 150 mg, with one injection of 1 mL for each of these doses.

Should this occur, the alternative investigational medicinal product will be maintained until the end of the study.

8.1.1 Route and method of administration

A manual for IMP administration (injection instruction manual) will be provided to patients containing detailed instructions on use, in particular for the patients having participated in the ODYSSEY Long Term study, for which the device was a prefilled syringe. Also, an administration package containing gauzes, alcohol swabs, band aids, etc. will be provided to the patients.

The IMP could be administered by self-injection or by another designated person (such as a spouse, relative, etc...). The used auto-injector will be discarded in a sharps container which will be provided to patients. It is recommended that the subcutaneous IMP injections be rotated within an anatomical area (eg, right thigh then left thigh or right abdomen then left abdomen). Patients also have the option to inject in a different anatomical area (eg, thigh then abdomen) during the study.

If another concomitant drug is being injected at the same site planned for the IMP injection, then the patient should be advised to use an alternate location for administration of the IMP.

Patients will be asked to store the IMP in a refrigerator. Prior to administration, the IMP should be set outside in a safe location at room temperature for about 30 to 40 minutes. Thereafter, the IMP should be administered as soon as possible.

Instructions as outlined above should be provided to the patient (or another designated person [such as spouse, relative, etc...] that will administer the injections) at training and as needed during the course of the study. Close supervision and feedback should be given at the first visit, and other visits as needed. Anyone that plans to administer the IMP must be trained by the study staff.

8.1.2 Timing of administration

On Day 1, visit 1, patients from the ODYSSEY Long Term study will have the possibility to perform a placebo, self-injection training using an auto-injector, before the first alirocumab injection.

On the same day, the first alirocumab injection will be done at the site by the patient or another designated person (such as spouse, relative, etc) under direct site staff supervision. Patients will be monitored at the investigational site for at least 30 minutes after this first injection in this study.

Alirocumab subcutaneous injections will then be performed outside of the clinic, every two weeks up to the last injection planned in the protocol. If the injection is scheduled to take place on the same date as the site visit, then the IMP should be administered after the blood sampling has been completed.

Alirocumab should ideally be administered subcutaneously every two weeks at approximately the same time of the day. The time of the day is based upon patient's preference; however it is acceptable to have a window period of \pm 3 days.

If by mistake or due to other circumstances an injection is delayed:

- by more than 7 days or completely missed, then the patient should return to the original schedule of study treatment administration without administering delayed injections.
- by less than or equal to 7 days from the missed date, then the patient should administer the delayed injection and then resume the original schedule of study treatment administration.

8.2 NON-INVESTIGATIONAL MEDICINAL PRODUCTS

The following classes of drugs are identified as non-IMP because the medication is either a background therapy or a potential rescue medication:

- Statins
- Cholesterol absorption inhibitors (ezetimibe)
- Bile acid-binding sequestrants (such as cholestyramine, colestipol, colesevelam)
- Nicotinic acid
- Fenofibrate
- Omega-3 fatty acids (≥1000 mg daily)

Please see Section 8.8 for further information.

8.3 BLINDING PROCEDURES

From Day 1 (visit 1) until Week 8 (first unblinded LDL-C value),

- neither the treatment received during the double-blind treatment period of the parent study,
- nor the lipid parameters levels,

will be known by the Investigator and by the patient, in order to prevent any potential to jeopardize the blinding of the parent clinical study.

From Week 8 (visit 3), the lipid parameters values will be communicated to the Investigator in real time.

8.4 METHOD OF ASSIGNING PATIENTS TO TREATMENT GROUP

This is an open-label study and every patient will receive alirocumab. Treatment kit numbers will be allocated via interactive voice/web response system (IVRS/IWRS). Patients will keep the same identification number that they were allocated in the parent study.

From Week 12 (Visit 4), the Investigator will manage, based on his/her own judgment and LDL-C value from sample obtained at the previous scheduled visit, adjustment of alirocumab doses (either up-titration from 75 mg to 150 mg every 2 weeks or down-titration from 150 mg to 75 mg every 2 weeks, or maintenance of the dose, will be possible). For adjustments based on LDL-C values, simultaneous adjustments in alirocumab dose and any LMT should be avoided.

8.5 PACKAGING AND LABELING

Each alirocumab treatment kit will be prepared to contain 6 auto-injectors in a child-resistant package.

Property of the Sanofi Group - strictly confidential

In addition to the alirocumab treatment kits, a training kit containing 1 placebo auto-injector will be prepared for the purpose of instructing patients on injection administration, in particular for patients originating from the ODYSSEY Long Term study.

The content of the labeling is in accordance with the local regulatory specifications and requirements.

8.6 STORAGE CONDITIONS AND SHELF LIFE

The IMP will be stored in a refrigerator between +2°C and +8°C (36°F to 46°F) by the site. The temperature of the site refrigerator should be checked daily and recorded on a log sheet.

The IMP that will be stored at the investigational site should be kept in an appropriate locked room, under the responsibility of the Investigator or designee or other authorized person in accordance with the storage conditions indicated on the label.

After the supply of IMP kits to patients at the study site visits, appropriate provisions will be in place for transportation of the IMP kits from the study site to the patient's refrigerator.

8.7 RESPONSIBILITIES

The Investigator, the hospital pharmacist, or other personnel allowed to store and dispense the IMP will be responsible for ensuring that the IMP used in the clinical trial is securely maintained as specified by the Sponsor and in accordance with applicable regulatory requirements.

All IMP will be dispensed in accordance with the Investigator's prescription and it is the Investigator's responsibility to ensure that an accurate record of IMP issued and returned is maintained.

Any quality issue noticed with the receipt or use of an IMP (deficiency in condition, appearance, pertaining documentation, labeling, expiration date, etc) should be promptly notified to the Sponsor. Some deficiencies may be recorded through a complaint procedure.

A potential defect in the quality of IMP may be subject to initiation of a recall procedure by the Sponsor. In this case, the Investigator will be responsible for promptly addressing any request made by the Sponsor, in order to recall IMP and eliminate potential hazards.

Under no circumstances will the Investigator supply IMP to a third party, allow the IMP to be used other than as directed by this clinical trial protocol, or dispose of IMP in any other manner.

8.7.1 Treatment accountability and compliance

IMP administration data will be recorded by the patients onto a patient's diary.

Measures taken to ensure and document IMP compliance and accountability are described below:

- The Investigator or designee will obtain via IVRS/IWRS the treatment kit number(s) and he/she will dispense the treatment kit(s) to the patient.
- The accountability is to be performed at IMP kit re-supply visits only (see Section 10.1.1). The used kit(s) and unused auto-injector(s) should be brought back to such visits for accountability purposes.
- The Investigator or designee will complete the corresponding treatment log form from patient's diary.
- The Investigator/study coordinator will enter data in the appropriate e-CRF pages, according to data recorded in the treatment log form.
- The monitor will check the data consistency between e-CRF pages, treatment log forms using patient's diary, and returned unused auto-injectors of a corresponding kit.

8.7.2 Return and/or destruction of treatments

A detailed treatment log of the destroyed IMP will be established with the Investigator (or the pharmacist) and countersigned by the Investigator and the monitoring team. The Investigator will not destroy the unused IMP unless the Sponsor provides written authorization.

If the site is not able to destroy or destruction of IMPs are not allowed in the country, all treatments kits will be retrieved by the Sponsor. A detailed treatment log of the returned IMP will be established with the Investigator or designee and countersigned by the Investigator and the Monitoring Team.

8.8 CONCOMITANT MEDICATION

A concomitant medication is any treatment received by the patient concomitantly to the study drug until the end of the patient's participation in the study.

Concomitant medications should be kept to a minimum during the study. However, if these are considered necessary for the patient's welfare and are unlikely to interfere with the IMP, they may be given at the discretion of the Investigator, with a stable dose (when possible). Besides the specific information related to concomitant medications provided in this section, any other concomitant medication(s) will be allowed and will have to be recorded in the e-CRF and source data.

8.8.1 Management of background lipid-modifying therapy

Throughout the whole treatment period, the patients should stay, as far as possible, on the stable maximally tolerated registered daily dose of statins, with or without other LMT, that was received during the parent study.

Background LMT may be adjusted as per the Investigator's judgment, for example in case of tolerability issue. Any adjustment will be documented in the e-CRF. For adjustments based on LDL-C values, simultaneous adjustments in alirocumab dose and any LMT should be avoided.

For background LMT, including statins, sites must follow the national product label for the safety monitoring and management of patients.

Lipid profile values from samples obtained after inclusion will be blinded until week 8.

8.8.2 Contraception

Women of childbearing potential must use an effective contraceptive method throughout the study treatment, and for 10 weeks after the last IMP injection for those patients who discontinue prematurely.

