9 ASSESSMENT OF INVESTIGATIONAL MEDICINAL PRODUCT

9.1 PRIMARY SAFETY ENDPOINTS

The safety parameters (adverse events, laboratory data, vital signs) will be assessed throughout the study.

The definition and reporting procedures of Adverse Events (AE), Adverse Events of Special Interest (AESI) and Serious Adverse Events (SAE) and management of specific laboratory abnormalities are described in sections 10.4 to 10.6.

Adverse event observation period:

The observation of safety data will be as follows:

- Pre-treatment observation period is defined as the time from signing the informed consent to the time of first dose of alirocumab in the current study. The adverse events occurring during this period will be reported and recorded in the parent study data base.
- TEAE period: the TEAE (Treatment Emergent Adverse Event) observation period is defined as the time from first dose of alirocumab in the OLE up to 70 days (10 weeks) after the last dose of alirocumab received in the OLE study for the patients who will either complete the study or who will prematurely discontinue, as residual effect of treatment is expected until 10 weeks after the stop of alirocumab.
- Post-treatment period: the post-treatment observation period is defined as the time starting the day after the end of the TEAE period up to the end of the study (see definition in section 6.2.1).

Death observation period:

The death observations are per the observation period defined above. In addition, "post-study" death includes all deaths reported after the end of the study (see definition of end of study period per patient in Section 6.2.1).

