10.1.1.17 End-of-treatment visit: Visit 17/ Week 168/ Month 40 (Day 1177± 7)

The end of study is scheduled to be in second quarter 2017 or when the drug will become commercially available for the patient in the respective country whatever comes first. Thus, the End-of-treatment visit might be performed earlier than on Week 168 according to the date of inclusion of each patient in the OLE study, or if the patient early discontinues the study.

- Collect adverse events
- Record concomitant medication
- Take vital signs including heart rate and blood pressure
- Get body weight measurement
- Physical examination
- Review patient's diet. Patient should be on a NCEP-ATPIII TLC diet or equivalent.
- Data collection on IMP administration and IMP compliance check by review of diary and treatment kit
- IVRS/IWRS contact to document the end of treatment
- Obtain fasting blood sample for:
 - Lipids: measure and/or calculation of total-C, LDL-C, HDL-C, TG, non-HDL-C, Apo B, Apo A-1, ratio Apo B/Apo A-1, and Lp (a)

- Hematology
- Chemistry
- CPK
- Liver panel
- Anti-alirocumab antibodies

- Local urine pregnancy test (females of childbearing potential only).
- Completion of EQ-5D questionnaire by patient.
- Reminders
 - For all the patients, those who prematurely discontinue the treatment irrespective of the reason and those who will complete the study, an appointment will be given for the Follow up call. This phone call will have to be scheduled 10 weeks after last injection (+/- 7 days).

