10.1.2 Post-treatment Follow up period

End of Study Phone call: Visit 18/ Week 176 (\pm 7 days)

This phone call is to be done for all the patients, those who discontinue the treatment prematurely, whatever the reason, and those who will complete the study, and will take place approximately 10 weeks after the last injection of alirocumab.

- Collect adverse events
- Record concomitant medication, including any commercially available PCSK9 inhibitor different from alirocumab
- IVRS/IWRS contact to document the end of study

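### Protocol 8.8.2 gives the 10-week post-injection contraception rule only to early discontinuers, while the note to E 08 gives it to every woman of childbearing potential

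*Protocol*

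**What the plan says.** Two places in the protocol state how long women of childbearing potential must use contraception.

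- **Note to E 08 (section 7.2.3):** "throughout the entire duration of the study treatment, and for 10 weeks after the last injection of IMP". The note makes no distinction between women who complete and women who stop early.
- **Section 8.8.2 (Contraception):** throughout study treatment, "and for 10 weeks after the last IMP injection for those patients who discontinue prematurely". Completers are not mentioned.

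Elsewhere the protocol handles the weeks after the last injection in the same way for both groups. Section 6.1 plans "A post-treatment safety follow up period of 10 week-duration after last IMP injection for all the patients". Section 9.1 sets the treatment-emergent period at 70 days after the last dose "for the patients who will either complete the study or who will prematurely discontinue, as residual effect of treatment is expected until 10 weeks". Section 10.1.2 says of the end-of-study call: "This phone call is to be done for all the patients, those who discontinue the treatment prematurely, whatever the reason", and goes on to include those who complete.

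**The concern.** A rule meant to protect participants is stated twice with different scope, and the narrower version sits in the section whose title is Contraception. E 08 is applied at entry, at Visit 1. The question of when a woman may stop contraception arises at the end of treatment, up to 168 weeks later, and 8.8.2 is the natural place to look then. Because it names only early discontinuers, a reader could infer that completers are released once treatment ends.

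At stake is exposure of a possible early pregnancy to residual drug during the weeks in which the protocol itself expects an effect. The point matters most for women who complete through the second route in section 6.2.1, reaching the second quarter of 2017 with alirocumab still not on sale in their country. They stop the drug with no commercial supply at home.

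**Working it through.** This is mainly a comparison of texts. The plan states no figure to reproduce.

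**Step 1: the two rules side by side.**

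| Patient group | Note to E 08 | Section 8.8.2 |
|---|---|---|
| Early discontinuers | treatment + 10 weeks after last injection | treatment + 10 weeks after last injection |
| Completers | treatment + 10 weeks after last injection | treatment only; nothing stated afterwards |

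The rules agree for early discontinuers and differ for completers.

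**Step 2: which wording fits the rest of the protocol.** The reason given in section 9.1 for the 70-day window is residual effect after the last dose. That depends on the date of the last injection, not on why injections stopped, and section 9.1 names both groups. Sections 6.1 and 10.1.2 also apply 10 weeks to both. The SAP (section 2.1.4, Observation period) repeats the residual-effect reason without separating the groups. Nothing in either document supports a shorter contraception period for completers, so 8.8.2 is the section to correct.

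**Step 3: length of the gap for a completer if 8.8.2 is read alone.**

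Inputs:
- End of contraception under E 08: 10 weeks × 7 = day 70 after the last injection.
- End of study treatment: 8.8.2 does not define it. It can be taken as the last injection (day 0), or as day 14. Day 14 is the end-of-treatment visit for completers in section 6.2.1 ("An EOT visit will be done 2 weeks after the last IMP injection and a safety follow up call 10 weeks after" the last injection) and the end of exposure in section 11.4.1.1, which adds 14 days to the last injection date.

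Gap = 70 − day on which treatment ends:
- treatment ends at the last injection: 70 − 0 = **70 days** (10 weeks)
- treatment ends at day 14: 70 − 14 = **56 days** (8 weeks)

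With the ±7-day visit window in section 1.2, the end-of-treatment visit falls between day 7 and day 21, and the interval from that visit to day 70 is 70 − 21 = 49 to 70 − 7 = 63 days.

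**Step 4: whether a scheduled test covers the same weeks.** The flow chart (section 1.2) and section 10.1.1.17 place the last urine pregnancy test at the end-of-treatment visit. The call at 10 weeks (section 10.1.2) lists adverse events, concomitant medication and the IVRS/IWRS contact, with no pregnancy test. The same 56 days (49 to 63) therefore have no scheduled test. This is true under either wording of 8.8.2. It is background and not part of the inconsistency.

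**The case against.** The strongest reply is that completers do have the rule. The E 08 note is mandatory, makes no split, and must be applied by every site at Visit 1. A site that follows it satisfies both sections, so the two do not collide in practice; 8.8.2 is silent on completers rather than exempting them. The 56 to 70 days arise only if a site relies on 8.8.2 and overlooks E 08, and the documents do not show that any site would. What women were told is in the consent form and local addenda, which were not available. The documents give no embryo-fetal risk data, and some completers will move to commercial alirocumab. A pregnancy in these weeks that came to the site's attention would still be captured, since section 10.4.4.1 makes it an event of special interest with immediate notification and follow-up to outcome. Finally, sections 6.1, 9.1 and 10.1.2 concern safety follow-up, so only E 08 states a competing contraception rule.

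Most of this stands as a limit on the size of the problem. The rule is not missing from the protocol, the gap is conditional on how 8.8.2 is used, and the testing schedule is a separate design choice that the correction would not alter. It does not remove the discrepancy. No text corrects 8.8.2, and capturing a pregnancy after the fact does not replace preventing one. Although the follow-up sections are not contraception rules, they supply the only stated reason for 10 weeks, and that reason covers completers.

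**Conclusion.** The point holds. Section 8.8.2 is narrower than the note to E 08 and is incomplete when read alone. For a woman who completes and stops the drug, it omits a contraception requirement lasting 70 days after the last injection, or 56 days if study treatment is taken to run to day 14.

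This rests on three conditions: that a site works from 8.8.2 without going back to E 08, that the woman does not continue on commercial alirocumab, and that the consent form or a local addendum does not already state the full rule. The number of women affected cannot be derived from the documents. Endpoints, data collection, pregnancy reporting and all statistical analyses are the same under either wording. It should be fixed because it is an operative participant-safety instruction and the correction is very small.

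**What to change.** In section 8.8.2, delete the words that restrict the 10 weeks to patients who discontinue prematurely. The section then matches the note to E 08: contraception throughout study treatment and for 10 weeks after the last IMP injection, for all women of childbearing potential. Check that the consent form and any local addenda give the same rule.

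The cost is one phrase in the next protocol amendment plus the document check. The visit schedule, data collection and SAP need no change.
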